### 2.2 Secondary Objectives

2.2.1 Compare the proportions of WOC vs non-WOC EAQ201 participants with COVID-related change in their material condition, a composite measure.

2.2.2 Compare the proportions of WOC vs non-WOC EAQ201 participants with COVID-specific perceived financial distress.

2.2.3 Compare the proportion of WOC in TMIST participants vs EAQ201 participants. A key hypothesis (now 2.2.3) is that financial hardship preferentially affects WOC and therefore their participation in TMIST. In order, to test this hypothesis, we need to compare the proportion of WOC who participated in TMIST compared to those who declined to participate in TMIST (estimated by EAQ201 participants).

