
TABLE 1 : Participant-completed items	
Primary Endpoints	Measure (collected from EAQ201 participants)
COVID-related financial hardship among EAQ201 participants	Composite outcome, defined as answering in the affirmative to any of the following personal changes due to COVID: layoff or furlough, insurance loss, work hours reduction, new job/increased hours to increase income, food or housing insecurity (items used in EAQ162CD) OR answering in the affirmative to any of the following household changes due to COVID: ≥20% income loss, savings use for living expenses, home sale/refinance, increased debt, declared bankruptcy (items used in EAQ162CD)
Secondary Endpoints	Collected from EAQ201 participants
Material condition composite measure	Self-reported material condition of any of the following: >20% income loss, savings use, home sale or refinance, loans, reaching credit limits, becoming subject to a collection agency, or bankruptcy in the last 3 months (binary) (1 item, used in EAQ162CD)
COVID-specific perceived financial distress	Adapted from the summary item from COST measure.  (continuous) “COVID-19 has been a financial hardship to my family.” (1 item)
Exploratory Endpoints	Collected from EAQ201 participants
Employment change	Self-reported work hours reduction, layoff or furlough, sick time or vacation time use or new job/increased hours to increase income (binary) (1 item, used in EAQ162CD)
COVID-specific perceived distress	Adapted from [name] (personal communication) to capture the emotional response to COVID related to fear of infection, financial anxiety, housing and food insecurity (single items). (categorical)(11 items)
Perceived susceptibility to disease	Single items for breast cancer and COVID-19, modified from previous studies of intention to undergo breast cancer screening and used in EA2185 and EAQ162CD. (categorical) (2 items)
Distress coping behavior that increase breast cancer risk	We previously demonstrated that risky behaviors (e.g., cancer screening adherence, not smoking and seatbelt use  ). Alcohol  use has been described a risk factor for breast cancer. Smoking  has been raised as a risk factor. We will assess change in frequency or amount of tobacco or alcohol use during COVID compared to before COVID. We will not assess absolute amount of use. (categorical) (2 items)

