#### 7.1.2 Secondary Objectives

7.1.2.1 Compare the proportions of WOC vs non-WOC EAQ201 participants with COVID-related change in their material condition, a composite measure.

Hypothesis: Compared to non-WOC, WOC will experience more COVID-related change in their material condition.

7.1.2.2 Compare the proportions of WOC vs non-WOC EAQ201 participants with COVID-specific perceived financial distress.

Hypothesis: Compared to non-WOC, WOC will experience more COVID-specific perceived financial distress.

7.1.2.3 Compare the proportion of WOC in TMIST participants vs EAQ201 participants.

Hypothesis: The proportion of WOC should be higher in the TMIST decliners than that in TMIST agree-ers.

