## 7.6 Gender and Ethnicity

Based on TMIST data from participants enrolled in September 2020, at sites in the United States, the anticipated accrual in subgroups defined by gender and race is:

Racial Categories	Not Hispanic or Latino Female	Not Hispanic or Latino Male	Hispanic or Latino Female	Hispanic or Latino Male	Total
American Indian/ Alaska Native	2	0	0	0	2
Asian	19	0	0	0	19
Native Hawaiian or Other Pacific Islander	1	0	0	0	1

Racial Categories	Not Hispanic or Latino Female	Not Hispanic or Latino Male	Hispanic or Latino Female	Hispanic or Latino Male	Total
Black or African American	196	0	2	0	198
White	742	0	30	0	772
More Than One Race	6	0	2	0	8
Total	966	0	34	0	1,000

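### As written in Table 1, the secondary material-condition composite does not match objective 2.2.1: it states no COVID attribution, looks back 3 months, and is not a strict subset of the primary composite

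*Combined protocol and SAP*

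**What the plan says.** Section 2.2.1 sets the secondary objective: "Compare the proportions of WOC vs non-WOC EAQ201 participants with COVID-related change in their material condition, a composite measure". Section 7.1.2.1 attaches the hypothesis "Compared to non-WOC, WOC will experience more COVID-related change in their material condition".

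The operational definition is in Section 5, Table 1, under the secondary endpoints. The row opens with "Self-reported material condition of any of the following: >20% income loss, savings use, home sale or refinance, loans, reaching credit limits" and its list ends with "home sale or refinance, loans, reaching credit limits, becoming subject to a collection agency, or bankruptcy in the last 3 months"; it is marked as one binary item taken from EAQ162CD. COVID is not mentioned in it. Section 7.3 tests this endpoint with a two-sample proportion test, makes covariate adjustment optional, and adds no attribution rule.

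The primary row of the same table has a personal block and a household block, both tied to COVID. The household block covers "household changes due to COVID: ≥20% income loss, savings use for living expenses, home sale/refinance, increased debt, declared bankruptcy". It sets no look-back period.

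Three other places bear on the construct. Section 2.1.1 makes change in material condition one of the components of the primary composite. Section 1.2 describes material condition as loss of income, employment or insurance. Table 3 (Section 6) heads the financial block of the survey as covering both financial situation and COVID-related change, with at most 7 questions.

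**The concern.** The objective and the endpoint describe different quantities. The objective asks about change caused by the pandemic. The endpoint, taken as written, counts any listed financial event in the last 3 months, whatever its cause. Reporting the second under the name of the first would label ordinary borrowing, refinancing or use of savings as COVID-related, and could leave out losses from early in the pandemic.

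Two things follow. If non-COVID events are equally common in both groups, they shrink the difference; if they differ between groups, they bias it, and adjustment is only optional. In addition, a reader would expect the secondary to be the material part of the primary, because Section 2.1.1 builds the primary from it. With two different definitions, the secondary cannot be used to explain a primary result.

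Table 1 describes the measure as a single binary item. If it is stored as one yes/no answer, non-COVID events cannot be separated out afterwards, so the definition has to be settled before analysis.

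**Working it through.** **Step 1. The two Table 1 rows side by side.**

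| Feature | Primary, household block | Secondary, material condition |
|---|---|---|
| Attribution | due to COVID | none stated |
| Look-back | none stated | last 3 months |
| Income loss | ≥20% | >20% |
| Savings | used for living expenses | any use |
| Debt | increased debt | loans |
| Home sale/refinance | yes | yes |
| Bankruptcy | yes | yes |
| Credit limits | not listed | yes |
| Collections | not listed | yes |

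Of the seven secondary events, three have a close match (income loss, home sale/refinance, bankruptcy), two are worded differently (savings, debt) and two are not listed in the primary. The provider-delay row of Table 1 has a 3-month window and also states that the delay is due to COVID, so the table can carry both qualifiers when both are meant.

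**Step 2. Nesting.** For the secondary to be a strict subset, every woman positive on it must be positive on the primary. A woman whose only event is a loan last month for a reason unrelated to COVID is positive on the secondary and negative on the primary, so the subset relation fails. In the other direction, a woman whose only event is a 40% income loss due to COVID in April 2020, surveyed in October 2020, is positive on the primary and negative on the secondary. So is a woman whose only event is a loss of exactly 20%. The secondary therefore does not capture the whole material component either.

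**Step 3. The window.** A 3-month look-back reaches 3/11/20, the protocol's pandemic reference date, only for surveys up to 6/11/20. Any survey after the end of July 2020 excludes all of April 2020, the month of the unemployment figures used for planning in Section 7.2. No activation date is given. Section 7.6 is "Based on TMIST data from participants enrolled in September 2020". If surveys began in or after that month (an assumption), the window starts no earlier than June 2020 and misses March to May 2020.

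**Step 4. Possible dilution, as an illustration.** No rate or power is stated for this endpoint; the nearest stated figures are those of Table 4, for the primary. Full enumeration of the two binomials with a two-sided Fisher's exact test at alpha 0.05 gives 0.777 (stated 0.77) for 0.20 vs 0.10 with 100 vs 900 women, and 0.886 (stated 0.88) for 0.18 vs 0.10 with 250 vs 750. All 12 rows of Table 4 reproduce within 2 points.

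Now take Table 4's rates as the true COVID-related rates p, and assume an independent share b of women in each group is positive for a non-COVID reason. The observed rate is q = b + (1 − b)p, so the difference shrinks by the factor (1 − b). For example, with b = 0.10: 0.10 + 0.90 × 0.20 = 0.28 and 0.10 + 0.90 × 0.10 = 0.19, a difference of 0.09.

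| b | 100 vs 900: rates | Power | 250 vs 750: rates | Power |
|---|---|---|---|---|
| 0 | 0.20 vs 0.10 | 0.78 | 0.18 vs 0.10 | 0.89 |
| 0.10 | 0.28 vs 0.19 | 0.53 | 0.262 vs 0.19 | 0.65 |
| 0.20 | 0.36 vs 0.28 | 0.37 | 0.344 vs 0.28 | 0.46 |
| 0.30 | 0.44 vs 0.37 | 0.26 | 0.426 vs 0.37 | 0.33 |

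If instead b = 0 and the window catches only 75% or 50% of COVID-related events in both groups, power is 0.65 or 0.48 (100 vs 900) and 0.77 or 0.58 (250 vs 750).

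**The case against.** The strongest reply is that Table 1 is a summary and not the instrument. Section 5 says so, calls the instrument a COVID factors survey, and Table 3 puts COVID-related change in the heading of the financial block. The employment row of Table 1 also omits attribution although objective 2.3.1 is about COVID-related employment change, which looks like shorthand. This stands as a limit. A reader might infer that the survey collects no COVID attribution at all; the documents do not show that, because the questionnaire is not among them. It does not rescue Table 1: a block heading does not define an endpoint, and if the item does carry attribution, the row still needs correcting.

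A second reply is that a recent window is defensible. It limits recall error and is close to the decision to decline TMIST, and objective 2.2.1 does not name spring 2020. That is a fair case for a window, but not for dropping attribution. Grammatically the 3 months could attach to bankruptcy alone; the natural reading covers the whole list, and the ambiguity itself needs removing.

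A third is that the item lists overlap and Section 2.1.1 names a concept without demanding strict nesting. Agreed: the accurate statement is that the secondary is not a strict subset as written, not that the two are unrelated.

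A reader might also argue that counting refinancing tilts the comparison by home ownership. The primary row contains the same item and so would the replacement, so this does not separate the two definitions.

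**Conclusion.** The point holds as a mismatch between a stated objective and its only operational definition. Objective 2.2.1 and hypothesis 7.1.2.1 concern COVID-related change; the Table 1 row does not say so, adds a 3-month window on its natural reading, and departs from the primary's household block on income cut-off, savings, debt and items. It should be corrected before analysis. The primary endpoint and Table 4 are not affected, and Sections 7.1.2 and 7.3 do not rank this secondary above the others.

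Two stronger readings are not supported. The first is that the trial loses a stated 77% or 88% power: those figures belong to the primary, and the falls shown above depend on background rates of 10% to 30%, independent and equal across groups, for which the documents give no source. The second is that the window certainly misses spring 2020: this depends on an assumed survey start, and because the current text is an amended version, the September 2020 data in Section 7.6 need not predate the first survey.

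**What to change.** Define the 2.2.1 endpoint in Table 1 from the household items already listed for the primary, with the same attribution to COVID, the same reference period and the same ≥20% income threshold. Put credit limits and collections in both composites or in neither, so that the secondary becomes a strict subset of the primary. Align Section 1.2, which describes material condition through income, employment and insurance, and Section 2.1.1 with that single definition; the household block has no employment or insurance item, so Section 1.2 cannot stay as it is. Check the questionnaire wording at the same time. If the 3-month unattributed item is a separate question, keep it and report it as descriptive only.

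The cost is an edit to Table 1 and the matching sections, plus endpoint programming. No new question should be needed, since the COVID-attributed household items have to be collected for the primary; Table 3 does not show whether one or two sets of financial items are asked, so this must be confirmed. The downsides are a longer recall period and less direct comparability with the EAQ162CD item.

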HRQL	Participant-Reported Outcomes Measurement Information System (PROMIS)-10  10-item physical and mental health assessment. Sum of item responses (continuous) (10 items)
General anxiety	PROMIS Anxiety 4-item Short Form. Sum of item responses (continuous) (4 items)
Depression	PROMIS Depression 4-item Short Form. Sum of item responses (continuous) (4 items)
Covariates	
Sociodemographics collected from EAQ201 participants	Race/ethnicity, age, education, marital status, annual household income, insurance, ZIP+4* to estimate neighborhood SES the using the Area Deprivation Index 
Sociodemographics collected from women who participate in TMIST	Race/ethnicity, age, insurance, and ZIP

TABLE 1 : Participant-completed items	
Provider-initiated delay	Participant-reported provider-initiated service delay or reduced access for any health service and for screening mammography in the last 3 months due to COVID
TABLE 2: Study team collected items	
Federal-, State- and local-level	Medicaid coverage policies, COVID burden and shelter-in-place policies (initiation, duration and extent of implementation) including any changes during the study period. Local unemployment rates  during shelter-in-place estimated from ZIP+4 using Local Area Unemployment Statistics from the Bureau of Labor.

State-level variables: COVID burden is assessed as:

- 1) Maximum new cases and deaths reported in one day as of registration of the first participant in that state;
- 2) Total case numbers in the 3-month period following the World Health Organization classification as a pandemic on 3/11/20 (raw and population-adjusted values);
- 3) Number of days from 3/11/20 to peak single-day report of new cases;
- 4) Occurrence of a “second peak” defined as a subsequent wave of new cases from the previous maximum number of new cases;
- 5) Cumulative death/infection rates at the time of study activation.

This data will be derived from the states’ departments of health and the Centers for Disease Control and Prevention. We will also examine state statutes and regulations including:

- 1) Timing of initiation of shelter-in-place policies (defined as the number of days from 3/11/20);
- 2) Duration of policies (number of days from initiation to any relaxation of shelter-in-place policies); and
- 3) Medicaid coverage of COVID-related care.

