7.2 Primary Objective

The primary objective is to compare the proportion of WOC EAQ201 participants who experience COVID-related financial hardship vs non-WOC EAQ201 participants. The results, with and without adjustment for missing values (see [7.5](#)), will be compared as a sensitivity analysis. Logistic regression models, with and without stratification by WOC status, will be fit with financial hardship as the response variable to investigate other sociodemographics (e.g., age, marital status, insurance status) and state- and local-level factors (e.g., state COVID severity, shelter-in-place policies, state and local unemployment during shelter-in-place) as moderators.

Sample Size Considerations for the Primary Objective ([7.1.1](#)):

The primary objective is to compare the proportion of WOC EAQ201 participants who experience COVID-related financial hardship (see **Table 1** for definition) with the proportion of non-WOC EAQ201 participants who experience COVID-related financial hardship. The National Bureau of Economic Research estimated unemployment rates by race and ethnicity in April 2020, around shelter-in-place regulations. Unemployment in African-American and Latinx populations averaged 18% compared to Whites (13%). At a sample size of 1000 women who decline TMIST participation, we expect to recruit at least 10-25% WOC into this study. Assuming alpha of 0.05, we estimated power over a range of differences across various proportions (see **Table 4**). For instance, at a sample size of 1000 with 10% of WOC, we have 77% power to detect a minimum difference of 0.10 between two proportions (0.2 vs. 0.1); at a sample size of 1000 with 25% of WOC, we have 88% power to detect a minimum difference of 0.08 between two proportions (0.18 vs. 0.1). Please note that based on DCP-001, 16% of the women who declined TMIST were WOC. Accrual onto TMIST is expected to continue for another 4.4 years. Also based on DCP-001 and extrapolating to the Non-NCORP US sites, accruing 1,000 women to this study is achievable. We do not envision any danger that this study will close due to lack of accrual.

**Table 4: Estimated power for a two-sample proportions using Fisher's Exact test (two-sided). N1: # of WOC; N2: # of non-WOC**

Sample size (N)	N1/N2	P1 (WOC)	P2 (non-WOC)	Delta	Alpha	Power
(Sample size: 1000; N1/N2=1/9, i.e.,10% of WOC)						
1000	1/9	0.200	0.100	0.100	0.05	0.77
1000	1/9	0.225	0.100	0.125	0.05	0.90
1000	1/9	0.250	0.100	0.150	0.05	0.96

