### 7.4 Assess the effects of sociodemographic characteristics, and federal-, state- or local-level COVID-19 factors on TMIST participation, in WOC vs non-WOC.

For the exploratory objective ([7.1.3.5](#)), we will compare the effects of sociodemographic characteristics, federal-, state- or local-level factors (e.g. maximum number of COVID-19 cases, state unemployment during shelter-in-place, local unemployment during shelter-in-place) on TMIST participation, stratified by WOC vs non-WOC. We will fit a logistic regression model with TMIST participation status (EAQ201 participant or TMIST participant) as the response variable to investigate other sociodemographic (e.g., marital status, neighborhood SES, insurance type), federal-, state- or local-level factors (see **Table 2**). Regression modeling will be conducted with and without stratification by WOC vs non-WOC.

The analysis set will include the 1000 EAQ201 participants from this study and a corresponding number of TMIST participants, who will be randomly selected from the enrolled participants in the main TMIST study. The selection will be stratified by site and enrollment time. Assuming that the proportion of overall EAQ201 participants is from 0.20 to 0.50, **Table 5** below shows the power analysis of testing for the odds ratio in the logistic regression. The variables of interest can be continuous or categorical (binary). For instance, 2000 women (1000 EAQ201 participants versus 1000 randomly selected TMIST participants) achieves 90% power at a 0.050 significance level to detect a change in the proportion of EAQ201 participants from 0.50 at the mean of the testing variable to 0.538 when the value of the variable is increased to one standard deviation above the mean. This change corresponds to an odds ratio of 1.165. An adjustment was made since a multiple regression of the independent variable of interest on other independent variables in the logistic regression obtained an R-Squared of 0.10.

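### State COVID-burden measure 1 has no population denominator and is cut off at a different date in each state, so it depends partly on state size and study start date

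*Combined protocol and SAP*

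**What the plan says.** The state-level list that follows Table 2 in Section 5 defines five measures of COVID burden without ranking them.

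- Measure 1: "Maximum new cases and deaths reported in one day as of registration of the first participant in that state". No denominator is given.
- Measure 2: "Total case numbers in the 3-month period following the World Health Organization classification as a pandemic on 3/11/20 (raw and population-adjusted values"). This is a fixed window with an explicit adjustment.
- Measure 3: "Number of days from 3/11/20 to peak single-day report of new cases". This is a time, so it needs no denominator.
- Measure 4: whether a second peak occurred.
- Measure 5: "Cumulative death/infection rates at the time of study activation". This is stated as rates and read at one date for all states.

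The Table 2 row itself promises "COVID burden and shelter-in-place policies (initiation, duration and extent of implementation) including any changes during the study period", but none of the five measures is dated to the individual woman.

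Two analyses use these factors. Section 7.2 fits logistic models of financial hardship with moderators that include "state COVID severity, shelter-in-place policies, state and local unemployment during shelter-in-place", and does not say which burden measure stands for severity. Section 7.4 models TMIST participation and gives "maximum number of COVID-19 cases, state unemployment during shelter-in-place" among its examples.

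**The concern.** Measure 2 shows that the authors wrote population adjustment down where they intended it. Taken as written, measure 1 is therefore a count. A count of daily cases or deaths grows with the number of residents, so a large state scores higher than a small one with the same epidemic.

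The cut-off adds a second dependence. The maximum is taken up to the first registration in the state, a date set by the study's own site activation and recruitment.

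The Introduction hypothesizes that state and local COVID factors weigh more heavily on participation among WOC. If measure 1 enters the models, an association with hardship or participation could come from state size or start date and be read as an effect of COVID burden.

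**Working it through.** **1. The plan's own figure.** The documents give no figure for the burden measure. The nearest is Table 5A, for the model that would use it: 2000 women, 90% power, odds ratio 1.165 per standard deviation (SD), P = 0.50, R-squared 0.10, alpha 0.05 (taken as two-sided). The usual formula for a continuous covariate in logistic regression is

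N = (z_0.975 + z_0.90)² / [P(1−P) × (ln OR)² × (1−R²)]

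= (1.960 + 1.282)² / [0.25 × (ln 1.165)² × 0.90] = 2002.

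The stated 2000 reproduces, so the power table contains no arithmetic error. It does assume that the factor is measured without error.

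**2. Dependence on population.** Raw peak = peak incidence × population. With an assumed incidence of 50 per 100,000 per day and assumed populations of 1 and 20 million, the scores are 50/100,000 × 1,000,000 = 500 and 50/100,000 × 20,000,000 = 10,000. The ratio of 20 is simply the population ratio. This shows how the measure scales, not how large the distortion would be in the real states.

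**3. How much of the variation could be population.** Write log(raw peak) = log(population) + log(per-capita peak), treat the parts as independent, and call their SDs sp and sr. The population share of variance is sp²/(sp²+sr²), and the correlation of the raw with the per-capita log peak is sr/√(sp²+sr²). All SDs below are assumed.

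| sp | sr | Population share | Correlation with per-capita peak |
|---|---|---|---|
| 0.5 | 1.0 | 0.20 | 0.89 |
| 0.5 | 0.5 | 0.50 | 0.71 |
| 1.0 | 0.5 | 0.80 | 0.45 |
| 1.2 | 0.3 | 0.94 | 0.24 |

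The share exceeds one half only when sp exceeds sr.

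**4. Dependence on the cut-off.** Let M(t) be the largest daily value up to date t. For a later date t', M(t') ≥ M(t), with equality when no day in between exceeds the earlier peak. A later first registration can therefore raise the score but never lower it.

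**5. What a diluted measure does to power.** Suppose the recorded measure correlates rho with the burden that matters, and the remainder is unrelated to outcome. The log odds ratio per SD is then multiplied by rho, and power = Φ(√(2000 × 0.25 × 0.90) × rho × ln 1.165 − 1.960).

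| rho (assumed) | Odds ratio seen | Power |
|---|---|---|
| 1 | 1.165 | 0.90 |
| 0.9 | 1.147 | 0.83 |
| 0.7 | 1.113 | 0.62 |
| 0.5 | 1.079 | 0.37 |
| 0.3 | 1.047 | 0.16 |

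If the remainder (state size, start date) is itself related to outcome, the result is bias rather than dilution, and its direction cannot be stated from the documents.

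**The case against.** Several stronger readings are tempting, and the documents do not support them.

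- *That measure 1 is the lead burden measure.* It comes first in the list, and Section 7.4 mentions a maximum case count, but only as an example. Nothing ranks the five, and Section 7.2 names none.
- *That it mainly tracks population and start date.* This needs state data that the documents lack; the assumed range of 0.20 to 0.94 does not settle it. Start dates may also differ little: Section 5 strongly encourages activation within 30 days and expects enrollment to finish in a few months. If a state's peak has already passed, a later cut-off changes nothing.
- *That the burden measures as a group ignore population.* The adjusted version of measure 2 and the rates of measure 5 largely answer the size problem, and measures 3 and 4 need no denominator.
- *That all models should use burden in a short window before each woman's decision.* For Section 7.2 this does not fit. The Table 1 composite collects job, insurance, income and asset losses attributed to COVID, which build up over the pandemic; peak and cumulative burden are reasonable exposures for it. A window of this kind is relevant at most to Section 7.4. It also needs the date of decline, which may be up to six months before registration (Section 3.1.1) and is not among the items in Section 4.1 or the Section 6 calendar.
- *That participation in Section 7.4 must be confounded with state size.* TMIST comparators are sampled with stratification by site and enrollment time. With equal sampling fractions, state factors would be largely balanced between the two groups by design. That limits confounding, but it also hides any true main effect. The fractions are not stated, and the balance need not hold within WOC and non-WOC separately.

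These points narrow the issue but do not remove it. The definition of measure 1 still lacks a denominator and a common date, and site stratification of the TMIST sample gives no protection to the Section 7.2 models.

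**Conclusion.** The point holds in a limited form. As defined, measure 1 depends partly on state population and can depend on when the study started in the state. An association with it could not be cleanly attributed to COVID burden. That follows from the definition alone. The size of the effect does not: the variance shares and the power losses rest on assumed SDs and correlations.

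The consequences are confined to the moderator models in Section 7.2 and the exploratory analysis in Section 7.4. The primary WOC versus non-WOC comparison, its power in Table 4 and the secondary proportion tests do not use the measure. This is an inexpensive improvement to supporting analyses, not a threat to the main result.

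**What to change.** 1. In Section 5, define measure 1 as the maximum one-day number of new cases, and separately of deaths, per 100,000 state population, read at one calendar date for all states. Study activation, as in measure 5, would serve. If a registration-based cut-off is kept anywhere, say whether the first participant means EAQ201 or TMIST.
2. In Sections 7.2 and 7.4, name the burden measure that enters each model, and use the population-adjusted version of measure 2. Keep peak and cumulative measures for Section 7.2.
3. Optionally, for Section 7.4 only, add per-capita burden over a stated window before TMIST enrollment or decline as a supplementary exposure. Record the decline date, or use the registration date as a declared proxy. This would also give effect to the Table 2 wording on changes during the study.
4. State the comparator sampling fractions by site and enrollment time, and check whether they leave any state-level contrast to estimate.

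Items 1 and 2 cost a few lines of text and some data programming. The case and death sources are already planned, and measure 2 already requires state populations. Item 3 needs one more date per woman if the proxy is not used. None of the changes adds survey questions.
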